Secondary Study Objective	
To explore long-term efficacy of isradipine 5 mg twice daily to slow progression of disability between baseline and 36 months of treatment as measured by parameters that reflect long term disability in PD:
 
 1) Motor function (characterized by UPDRS Part III in the medications OFF state, UPDRS ambulatory capacity subscore, time to initiation of symptomatic therapy, time to onset of motor complications, dosage and utilization of symptomatic therapy, MDS-UPDRS Motor score) 2) Cognitive function as measured by the Montreal Cognitive assessment Scale (MoCA) 3) Global measures of disability as measured by modified Rankin score 4) Measures of functional status and quality of life (PDQ-39, MDS- UPDRS Motor and Non-Motor Experience of Daily Living)
Study Design	A randomized, Phase-3, 2-arm, double-blind, parallel group trial with subjects 1:1 randomized to 5mg of Isradipine IR twice daily or matching placebo twice daily.
Duration of Treatment	36 months on randomized treatment of 5mg of Isradipine IR twice daily or matching placebo.
Route and Dosage	Oral capsules Isradipine IR or matching placebo

Study Population	336 subjects with early idiopathic PD not requiring dopaminergic therapy
Study Inclusion Criteria	
 1. Subjects with early idiopathic PD (presence of at least two out of three cardinal manifestations of PD). If tremor is not present, subjects must have unilateral onset and persistent asymmetry of the symptoms 2. Age equal or greater than 30 years at the time of diagnosis of PD 3. Hoehn and Yahr stage less than or equal to 2 4. Diagnosis of PD less than 3 years. 5. Currently NOT receiving dopaminergic therapy (levodopa, dopamine agonist or MAO-B inhibitors) and NOT projected to require PD symptomatic therapy for at least 3 months from the baseline visit 6. Use of amantadine and/or anticholinergics will be allowed provided that the dose is stable for 8 weeks prior to the baseline visit 7. If subject is taking any central nervous system acting medications (e.g., benzodiazepines, antidepressants, hypnotics) regimen must be stable for 30 days prior to the baseline visit 8. Women of childbearing potential may enroll but must use a reliable measure of contraception and have a negative serum pregnancy test at the screening visit

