5.2.7 Study Drug Titration

Blood Pressure Monitoring:

1. All subjects will require home blood pressure monitoring for at least 7 days prior to baseline. Blood pressure monitoring continues during dose titration.
2. Using a home digital blood pressure device, subjects will obtain blood pressure readings at home twice daily in the morning and in the evening, approximately 12 hours apart. The blood pressure readings will be obtained in a sitting position and after 2 minutes in a standing position. Blood pressure recordings will be uploaded via internet access in real time to the BP Vendor. During drug escalation or de-escalation, site investigators and study staff will be blinded to home blood pressure recordings unless unblinding is warranted for subject safety. Home blood pressure recordings will be monitored remotely by an assigned BP Clinical Monitor who will have access to the BP vendor web-based database. The BP Clinical Monitor will communicate with the Site Investigator if needed to discuss drug titration management.
3. During drug titration, the BP Clinical Monitor will have access to the BP Vendor database and will assess home blood pressures out of range to include Systolic Blood Pressure less than 90 mmHg or greater than 160 mmHg and Diastolic Blood Pressure less than 60mmHg or greater than 90 mmHg.
4. Site Investigators and Coordinators will have limited access to the BP vendor web-based blood pressure database, in order to maintain the blind, and will be required to access the database prior to the Baseline visit and for each visit during drug titration to confirm titration can continue. The database will provide site staff with a confirmation notice to state that titration can proceed or cannot proceed. The Site Investigator and Coordinator will not be able to view BP data on the vendor website. See Section 13 of the operations manual for additional information on the site staff access to the website. Random delays

in dose titration may be done in both study groups (active or placebo) at the direction of the Biostatistician at the University of Rochester in order to preserve the study blinding.

5. For subjects where the BP vendor confirmation message states drug titration may proceed, confirmation of in-person blood pressure readings must also meet titration requirements as outlined in “*Rules for Study Drug Titration*” below.

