Interim tolerability analysis

An interim tolerability analysis will be performed after the first 60 subjects complete the titration period of the study (Visit 03 (Month 3). Tolerability will be defined as ability to achieve and maintain target daily dosage of study drug (10 mg) by the end of titration period. The tolerability threshold will be defined as more than 30% difference in the tolerability of the active treatment group relative to the placebo group. Only dosage reductions, discontinuations, and premature terminations due to intolerability will be included in the analysis, terminations for other reasons will not be included in this analysis. The study may be terminated if tolerability parameters are not met. These analyses will be conducted by the unblinded statistician and reported to the DSMB.

Interim analysis of the Pharmacokinetic (PK) data

An interim PK analysis will be performed (at steady-state) after the first 60 subjects who reach target daily dose of 10 mg complete the titration phase of the study to assure that serum concentrations fall within predicted range. C_{min} and C_{max} serum concentrations

will be analysed. Only data on the subjects who have reached 10mg dose of study drug (Isradipine IR or placebo) will be included in the interim analysis. Based on the data discussed in Section 2.1, we expect the C_{min} concentration to be 0.4±0.2 ng/ml (1 SD from the C_{min} mean). Thus C_{min} = 0.2 ng/ml should be established as the threshold of the therapeutic effect. In case mean C_{min} concentrations fall below 0.2 ng/ml, the following paradigm is proposed:

- 1) May validate the PK data by completing a full PK profile on a small sample of study subjects (N=6)
- 2) In case the AUC 0-12hr falls within the expected range (13.9± 6.1 ng/ml)(Holmes and Kutz 1993), the study will proceed as planned
- 3) In case AUC 0-12hr is below expected range the DSMB may seek independent assessment of the PK data by a clinical pharmacologist
- 4) In case the C_{min} values are below C_{floor} (0.25 nM (0.098 ng/ml)) – DSMB may consider an alternative dosing regimen

Interim futility and efficacy analysis

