C. *Sensitivity Analyses.* A variety of sensitivity analyses will be conducted to assess the robustness of the comparison between treatment groups.

- I. Non-parametric methods. Residual plots will be examined. In the event that these show outliers or pronounced non-normality, supplementary analyses will be performed after deletion of outliers and/or using appropriate non-parametric methods.
- II. Missing Data. Effects of missing data will be assessed (i) by multiple imputation and (ii) by “best case” and “worst-case” analysis and (iii) by the use of mixed models (which use intermediate study data to project final study outcomes when these are missing).
- III. Influence of Symptomatic Medication. Supplementary analyses of the final study outcomes will be conducted with current use of symptomatic medication (levodopa equivalents) added as an additional predictor variable. The purpose of this analysis is to assess whether any differences seen in the primary outcome variable could be attributed to differential use of symptomatic therapy between the treatment groups.

D. *Subgroup Analyses – Including Gender and Race/ Ethnicity*

Recognizing that the study will not have high power to detect treatment effects among subgroups, we will conduct exploratory analyses to check the consistency of treatment effects on the primary and secondary efficacy measures in relation to selected baseline characteristics, including gender and race/ ethnicity. The analysis will use two approaches (i) repeating the primary analysis for each subgroup (for example men and women; minority and non-minority) separately, (ii) inclusion of additional terms in the analysis of covariance model to represent the overall effect of the characteristic (do men progress faster than women?) and for the interaction of the treatment with the characteristic (does the effect of the treatment differ between men and women?). Results for each race/ethnic grouping will be tabulated separately.

5. Safety and Tolerability Analysis

A. *Primary Safety and Tolerability Outcomes.*

- I. The ability to complete the 36 months study on the originally assigned treatment dosage
- II. The proportion of subjects requiring dosage reductions secondary to intolerability
- III. The frequency of adverse events and serious adverse events
- IV. Laboratory and EKG abnormalities

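### The interim tolerability analysis defines success as reaching 10 mg daily but counts only reductions, discontinuations and terminations, so a subject held below 10 mg by low blood pressure fails the definition without being counted

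*Protocol*

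**What the plan says.** Protocol 8.1 (Interim tolerability analysis), repeated in SAP 8.B, sets out four things:

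- the definition: "Tolerability will be defined as ability to achieve and maintain target daily dosage of study drug (10 mg) by the end of titration period";
- the threshold: "The tolerability threshold will be defined as more than 30% difference in the tolerability of the active treatment group relative to the placebo group";
- the events that enter the comparison: "Only dosage reductions, discontinuations, and premature terminations due to intolerability will be included in the analysis", with terminations for other reasons left out;
- the consequence: "The study may be terminated if tolerability parameters are not met".

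Protocol 5.2.7 makes the step from 5 to 10 mg daily conditional on blood pressure. On the vendor site, "The database will provide site staff with a confirmation notice to state that titration can proceed or cannot proceed". The in-person readings must also meet the titration criteria. The same section asks sites to tell the coordination center (CTCC) within 24 hours when titration is reduced or suspended. Protocol 5.2.6 requires every subject to enter maintenance by Visit 03, and it allows random dose adjustments in either arm to protect the blind; 5.2.7 likewise allows random titration delays.

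Among the end-of-study outcomes, SAP 5.A item II is "The proportion of subjects requiring dosage reductions secondary to intolerability".

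**The concern.** The definition has two limbs, getting to 10 mg and staying there. The counted events cover losing a dose already held, stopping the drug, or leaving the study. None covers a subject who was never escalated. The protocol creates such subjects: when the blood pressure check fails, the subject stays on one capsule twice daily, with no reduction, discontinuation or termination to record.

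This is the only pre-set numerical tolerability threshold tied to possible termination of the study. Hypotension is among the mechanism-related effects that Protocol 2.5 lists for isradipine. If persistent holds are commoner on active drug, leaving them out of the failure count narrows the gap reported to the DSMB. SAP 5.A item II has the same blind spot, because a hold is not a reduction.

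**Working it through.** **Text check.** Classification of a subject below 10 mg daily at Visit 03:

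| Reason | Fails the definition? | Counted event? |
|---|---|---|
| Dose reduced for intolerability | Yes | Yes |
| Stepped down after a failed increase (Protocol 5.5) | Yes | Yes |
| Never escalated: low or orthostatic blood pressure | Yes | Not listed |
| Never escalated: blinding delay | Yes, literally | Not listed |

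The third row is the gap. The fourth shows why the repair cannot simply count everyone below 10 mg.

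**Inputs.**

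- Interim sample: "An interim tolerability analysis will be performed after the first 60 subjects complete the titration period of the study". Allocation (Protocol Synopsis): "subjects 1:1 randomized to 5mg of Isradipine IR twice daily or matching placebo twice daily". An even split of 30 per arm is assumed.
- Threshold: more than 30%. No derivation or error rate is given, so there is no planned figure to reproduce. An absolute scale is assumed, with the relative scale alongside.
- Failure rates (Protocol 2.6, phase II, completion without dosage adjustment): placebo 25/26 = 96.2% tolerant, so 1/26 failing; 10 mg 19/26 = 73.1% tolerant, so 7/26 failing. These come from the CR formulation over 52 weeks and are only a proxy for titration on IR.
- Share of otherwise tolerant active subjects still held at Visit 03, h: not given. Values of 5% and 10% are assumed for illustration.

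**Scale.** The phase II gap is 25/26 - 19/26 = 6/26 = 23.1 points absolute, or 1 - 19/25 = 24.0% relative. Neither exceeds 30%, so phase II does not show which scale is meant.

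**Worked count.** Each subject is worth 1/30 = 3.3 points. Take 1 placebo failure and 8 counted active failures, with 3 more active subjects held by low blood pressure:

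- holds not counted as failures: 29/30 - 22/30 = 23.3 points, not crossed;
- holds counted as failures: 29/30 - 19/30 = 33.3 points, crossed;
- held subjects dropped from the denominator: 29/30 - 19/27 = 26.3 points, not crossed.

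With 2 holds counted, the absolute gap is 29/30 - 20/30 = 30.0 points, not crossed. The relative gap is 9/29 = 31.0%, crossed. The unstated scale can therefore decide the result.

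**Chance of crossing.** Let the numbers tolerant be X_A ~ Bin(30, p_A) and X_P ~ Bin(30, p_P). A gap of 9/30 is exactly 30%, so crossing the absolute threshold needs X_P - X_A of at least 10. On the relative scale it needs X_P - X_A > 0.3 X_P. Put p_P = 25/26 and p_A = (19/26)(1 - h). As written, held subjects are taken as tolerant, which is the same as h = 0.

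| Case | p_A | P(absolute) | P(relative) |
|---|---|---|---|
| As written | 0.731 | 0.164 | 0.227 |
| 5% held and counted | 0.694 | 0.291 | 0.379 |
| 10% held and counted | 0.658 | 0.442 | 0.544 |

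**Sensitivity.** If 3.3% of otherwise tolerant placebo subjects are also held and counted, the absolute figures for 5% and 10% become 0.197 and 0.323, against 0.164 as written. If tolerability before holds is 87% (the open-label 10 mg CR figure in Protocol 2.6), they become 0.012 and 0.051, against 0.001 as written.

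**The case against.** The restricting sentence can be read as limiting causes rather than event types: its purpose would be to keep unrelated dropouts and blinding delays out, leaving the definition in charge. That reading is possible, but the list does not say it, and the analyst should not have to choose.

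The effect may be small. Phase II reported no significant effect on blood pressure, and reduction or suspension for it in 3 of 99 subjects, against 14 for leg edema alone. Those are not hold rates and come from the CR formulation, but they are the nearest evidence. Only holds lasting to Visit 03 matter. Before then, in-person readings may be repeated, concomitant antihypertensives may be reduced and titration may resume. Symptoms that lead to a dose reduction are counted.

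Other safeguards exist. Termination is permissive. The DSMB meets about every six months and sees vital-sign changes and clinical monitor actions on blood pressure alerts (SAP 8.E). SAP 5.A item I, completing 36 months on the assigned dosage, can capture a subject who never reached 10 mg, although it does not help the 60-subject interim.

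These points limit the size and the consequence. They do not remove the conflict.

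A reader might infer that blood pressure holds are the main way hypotension keeps subjects from 10 mg. The documents give no frequencies to support that.

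**Conclusion.** The definition and the counted events conflict in both documents, and neither settles how a held subject is classified or whether that subject stays in the denominator. The bias is toward tolerable only if persistent low-pressure holds are commoner on isradipine, which is plausible but not shown. On the illustrative inputs (30 per arm, absolute threshold, phase II CR rates, no placebo holds), the chance of crossing moves from 16% to 29% or 44%. With better underlying tolerability or some placebo holds the change is smaller.

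A reader might go further and take an active failure rate of 40%. The chance of crossing would then be 67.9% with every failure counted, falling to 47.5% or 26.8% if 5 or 10 points of it were uncounted holds. The arithmetic is correct, but no document gives a 40% rate, so these figures should not be used to size the problem. Nor do the documents support calling the safeguard disabled, since the DSMB sees other blood pressure data and the rule does not bind it. The change is still worth making, because it alters what a pre-set decision threshold counts.

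**What to change.** In Protocol 8.1 and SAP 8.B, reconcile the two sentences along these lines: a subject not on 10 mg daily at Visit 03 because of low or orthostatic blood pressure readings (home or in-person) or an adverse event is a tolerability failure, whether or not a dose reduction occurred. State also that:

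- all subjects who complete titration stay in the denominator;
- assigned blinding delays, holds for high blood pressure and terminations for other reasons are not failures;
- the 30% is absolute or relative, whichever is meant.

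The exclusion of high-pressure holds is needed because Protocol 5.2.7 also flags systolic readings above 160 and diastolic readings above 90 mmHg. If such readings block titration, counting those holds as intolerability could introduce a new bias. Make the matching addition to SAP 5.A item II, so that it also covers never reaching 10 mg for low or orthostatic blood pressure or an adverse event.

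The change is to analysis definitions only; no dosing or titration rule is altered. The wording is short, but some data work follows. The Dose Management Log records dose changes (Protocol 6.3.6), and a hold is not a change. Home readings are outside the study database (SAP 8.E). The reason for each hold would have to come from the titration-suspension notices to the CTCC and the clinical monitor's action records. The list of assigned blinding delays must be passed to the unblinded statistician. The active tolerability figure may look slightly less favourable.

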8.2 Outcomes

8.2.1 Primary Outcome

Efficacy:

Efficacy will be defined as the change in total UPDRS score between the baseline visit and month 36. Comparison will be made between active treatment arm and placebo. We expect that nearly all subjects will require symptomatic therapy (e.g. levodopa or dopamine agonist) prior to the end of the 36 months study. In that case UPDRS will be assessed in the medications ON state (based on the subject/ investigator defined BEST ON, approximately 1 hour after dose of symptomatic therapy).

Medications ON state was chosen based on the following rationale: if disease modifying effect of isradipine exists it will be sustained even in the medications ON state; the practical difficulty in withdrawing subjects; the persistent symptomatic benefit of symptomatic therapy even in the “defined medications OFF” state. In addition there are no pilot data on the longitudinal change of UPDRS in the medications OFF state over 36 months period in de novo population to allow power calculations.

Our primary efficacy analysis will use analysis of covariance applied to the change from baseline in the total UPDRS score. The baseline value will be entered into the model as a continuous variable, the assigned treatment and the enrolling Investigator will be entered as a stratification variable. The primary analysis will be based on the intent-to-treat principle and will include all subjects who have 36 month data. A two-sided test with $\alpha = 0.05$ will be used to declare statistical significance. Sensitivity analyses will be performed using data values imputed under various “missingness” mechanisms for the subjects who do not complete 36 months of follow-up. Consistency of results over study sites and with respect to major demographic and clinical baseline variables will be assessed descriptively and by appropriate tests of statistical interaction. We will also perform an exploratory analysis by achieved final dosage (0, 2.5, 5.0, 7.5 and 10.0) for the subjects assigned to active treatment.

8.2.2. Secondary Outcomes

Efficacy analysis (at 36 months):

The change in the following measures of disability from baseline to 36 months will be analyzed:

- I. Motor disability
 - a. The change in UPDRS Part III Motor subscale in the defined medications OFF state (approximately 12 hours after the last dose of symptomatic therapy for those subjects that have initiated symptomatic therapy)
 - b. MDS-UPDRS Motor score in the defined medications ON state (as per the primary outcome)
 - c. The change in the ambulatory capacity (sum of 5 UPDRS questions: falling, freezing, walking, gait, postural stability)
 - d. Time to initiation of symptomatic therapy
 - e. Proportion of subjects that start symptomatic therapy
 - f. Analysis of symptomatic therapy utilization as measured by levodopa equivalence dose[1]
 - g. Time to onset and severity of motor complications as measured by UPDRS IV subscale (complications of therapy) for those subjects that have initiated symptomatic therapy

For continuous measures, the analysis will proceed in the same way as for the primary outcome measure. Logistic regression will be used for the binary out-

come (e) and Cox's proportional hazards model for the time-to-event outcomes (d) and (g).

II. Cognitive disability

a. The change in the cognitive function as measured by the change in the MoCA [2, 3]

III. Measure of global disability

a. The change in the Modified Rankin score

IV. Measures of functional status and quality of life

a. The change in Activities of Daily Living (ADL) subscale of the UPDRS

b. The change in the MDS-UPDRS Part II

c. The change in the modified Schwab and England scale

d. The change in Parkinson Disease Quality of Life Questionnaire-39 (PDQ-39) [4]

e. The change in Neuro-QOL

f. The change in Non-motor and Motor Experiences of Daily Living scores of the MDS-UPDRS

While the primary outcome measure at 36 months is the change in the total UPDRS we also will explore the measures that reflect long term disability in PD including motor and cognitive function as well as global measures of disability and quality of life measures (as outlined below) between the baseline and 36 months of treatment. While 36 months is not a sufficiently long period of time to assess the impact of an intervention on such long term measures of PD disability as gait, balance, and cognitive function; the current analysis may provide a signal of efficacy that may be followed by a long term confirmatory study. We will also examine whether onset of disability requiring symptomatic treatment and early changes in total UPDRS and its components are useful predictors of long-term disability.

Safety and Tolerability Analysis:

1. The ability to complete the 36 months study on the originally assigned treatment dosage
2. The proportion of subjects requiring dosage reductions secondary to intolerance
3. The frequency of adverse events and serious adverse events
4. Laboratory and ECG abnormalities
5. An interim tolerability analysis will be performed after the first 60 subjects complete titration period of the study (Visit 03) as discussed in section 9.1

All subjects known to have received study treatment will be included in the safety analysis.

All adverse events and abnormal laboratory values results will be listed by treatment and be identified by subject and site. They will also be tabulated by treatment group, severity and perceived relationship to study drug. Fisher's exact test will be used to compare each

active treatment group to the placebo group with regard to the proportion of subjects experiencing a particular adverse event. Separate analyses will be performed excluding mild events and those categorized as unrelated to study drug. In all comparative analyses, events occurring after Baseline Visit will not be counted if the subject experienced the event at the Baseline Visit, unless the severity increases.

A similar approach will be adopted to compare out-of-range laboratory values between groups.

The following measures of the effect of the study drug on vital signs, specifically on orthostatic blood pressure will be analyzed:

- Changes in vital signs recorded at each visit.
- The proportions of subjects who develop orthostatic hypotension as defined by a drop in systolic blood pressure of greater than or equal 20 mm Hg and a drop in diastolic blood pressure of greater than or equal to 10 mm Hg when going from a sitting to a standing position.
- The proportions of subjects who develop symptomatic orthostatic hypotension, defined as orthostatic blood pressure changes, as defined previously, associated with presence of positional dizziness or other symptoms.

Comparisons of the active treatment group with the placebo will be made using one-sided Fisher's exact tests supplemented by tests of trend in proportions to examine exposure-response relations among the four groups.

Exploratory analysis:

An analysis of the correlation between clinical efficacy measures and plasma PK concentrations will be performed. The analysis will be based on correlation of the change of the efficacy measures and serum concentration of isradipine measured as AUC 0-12 hour based on the sparse PK profile collected during the study.

